DETERMINATION OF SERUM FENTANYL LEVELS AFTER USING REFERENCE AND GENERIC TRANSDERMAL FENTANYL PATCHES WITH AND WITHOUT STANDARDIZED HEAT APPLICATION IN HEALTHY HUMAN VOLUNTEERS

Short title: The Effect of Heat on Fentanyl Release from Fentanyl Patches in Healthy Adults

Clinical Protocol Principal Investigator:

[name], MS

U01 Principal Investigator(s):

[name] (contact), PhD

[name]

Sponsor:

Food and Drug Administration

Grant Number: 1U01FD004955-01

Protocol Number: HP-00059884

NCT02486016

Version 8.0 12 June 2017

CLINICAL STUDY STATISTICS

IVIVC

For IVIVC, three correlation levels were examined. Level A was selected to use for analysis of the data. Three different (I, II & III) approaches were examined for Level A.

Level A: a point-to point correlation between in vitro and in vivo profiles.

Level B: comparison between in vitro dissolution time and in vivo residence time.

Level C: a single point correlation between in vitro and in vivo parameters (e.g. J_{max} vs. C_{max}).

Approach I: IVPT data, PK-based mathematical equations and in vitro heat effect coefficient (H_i) were used to predict in vivo concentrations.

• Eq. 2 Prediction after TDS removal:

*R*_{in}: Rate of input (mean flux during steady-state in IVPT experiments)

H_i: In vitro heat effect coefficient (composite heat effect during and after heat exposure); ratio of flux values with heat and without heat

CL: Total body clearance obtained from literature/product package information

- k: Elimination rate constant obtained from literature/product package information (k₁: after IV dose; k₂: after TDS dose)
- t: Time after administration of TDS for Eq.1 and time after removal of TDS for Eq. 2

Co: Initial concentration after TDS removal

Approach II and III:

- 1. Reconstruct baseline (32°C) profile by combining the non-heat (32°C) portion of each profile from the early and late heat study designs.
- 2. Deconvolute the in vivo baseline concentration vs time profile using Phoenix®.
- 3. Construct an IVIVC model by plotting the fraction permeated in vitro vs the fraction absorbed in vivo.
- 4. Predict the in vivo fraction absorbed using the IVIVC model and IVPT data.

- 5. Convolute the predicted in vivo fraction absorbed data using Phoenix® to obtain concentration vs time profile
- 6. Apply in vitro heat effect coefficient H_i (Approach II) or the in vivo heat effect coefficient H_{ii} (Approach III) to the predicted in vivo profile.

Pharmacokinetic parameters of fentanyl used for Approach I, II and III were obtained from:

- Bower et al. Br J Anaesth 1982
- McClain et al. Clin Pharmacol Ther 1980
- Scott et al. J Pharmacol Exp Ther 1986
- Fung et al. J Clin Pharmacol 1980
- Study [NIPTE-U01-MD-2015-001: Transdermal Drug Delivery Systems-Fentanyl] at University of Maryland, Baltimore; *still in progress*
- *F* [absolute bioavailability for TDS] for Duragesic[®] (0.36) and Mylan (0.42) were each determined from study [NIPTE-U01-MD-2015-001: Transdermal Drug Delivery Systems-Fentanyl] at the University of Maryland, Baltimore
- *F* [absolute bioavailability for TDS] for Apotex was estimated (0.39) by the mean of 0.36 and 0.42, due to lack of available data

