2.2 Rationale

The objective of this proposal is to conduct in vivo studies to compare the influence of heat on fentanyl drug release from FDA approved TDDS products (reference e.g. Duragesic[®], versus generic products e.g. Apotex and Mylan transdermal patches) that have different inactive ingredients. While there is data in the literature for heat effect on different active pharmaceutical ingredients (API's), specifically reference listed drugs (RLD), from exposure to heating blankets, sauna, hot showers, exercising, there is no head to head comparisons for heat effect on RLD versus generic drugs. This study will help support policy development for characterization of heat effects for future generic applications. Furthermore, if in-vitro in-vivo correlation (IVIVC) can be established, then in vitro studies can be used for generic applications in the future, which would mitigate

exposure of human beings to out of label studies. This approach will help ensure that patients would not be subjected to additional risks if they use a generic TDDS rather than its respective reference product.

Fentanyl was selected for this study because it is a drug with significant and well characterized heat effect studies in the literature, and for which an antidote exists. Fentanyl has the most variability available in terms of generic transdermal systems with different formulations that are approved and already on the market. This study will provide data that could potentially help us determine if one formulation/adhesive is more prone to heat effect/changes in delivery compared to another. Furthermore by demonstrating IVIVC then in vitro studies can be conducted on generic fentanyl transdermal patches in the future without the need to subject human volunteers to additional testing. To mitigate the potential risk of a higher absorption of fentanyl through the skin, the lowest strength patch is being used in this study (25 µg/hr).

Duragesic® versus Apotex (fentanyl) and Mylan (fentanyl) transdermal patches

	Duragesic [®]	Apotex (fentanyl) patch	Mylan (fentanyl) patch
Inactive ingredients	Alcohol, ethylene vinyl acetate-copolymer	Isopropyl myristate, octyldodecanol, polybutene	Dimethicone NF, polyolefin film backing,
	membrane and hydroxyethyl cellulose, polyester film backing, silicone adhesive	and polyisobutene adhesive	silicon adhesive
TDDS type	Matrix	Matrix	Matrix
Manufacturer	Janssen	Apotex	Mylan

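### No planned step tests the heat coefficient in the IVIVC, and whole-profile correlation, the only standard named, is a weak test of it

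*SAP*

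**What the plan says.** The SAP (IVIVC) lists Levels A, B and C and states that "Level A was selected to use for analysis of the data". Level A is described as "Level A: a point-to point correlation between in vitro and in vivo profiles", and "Three different (I, II & III) approaches were examined for Level A". It sets no correlation threshold, no limit on prediction error, no check confined to the heat periods and no comparator.

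Heat enters the three approaches as follows.
- Approach I: "IVPT data, PK-based mathematical equations and in vitro heat effect coefficient (H_i) were used to predict in vivo concentrations".
- Approaches II and III, step 1: "Reconstruct baseline (32°C) profile by combining the non-heat (32°C) portion of each profile from the early and late heat study designs". Steps 2 to 5 deconvolute this baseline, relate fraction permeated to fraction absorbed, and convolute back.
- Approaches II and III, step 6, the last: an in vitro (II) or in vivo (III) heat coefficient is applied "to the predicted in vivo profile".

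The in vitro coefficient H_i is a "ratio of flux values with heat and without heat", meant to cover both the heating and the time after it. No value is given.

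Section 2.2 of the protocol gives the intended use: "by demonstrating IVIVC then in vitro studies can be conducted on generic fentanyl transdermal patches in the future".

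**The concern.** The scientific question is whether in vitro heat data predict the in vivo response to heat. The one standard named compares whole profiles. Heat lasts one hour of a 19-hour wear, so for a slowly eliminated drug most of the agreement comes from the rise during wear and the fall after removal, which any reasonable unheated model reproduces.

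In Approaches II and III the fitted correlation describes the 32°C baseline, so its quality cannot support the coefficient added afterwards. A high correlation could then be read as showing that in vitro heat testing works when heat prediction has not been examined. That reading would bear on the proposal to spare volunteers in future generic applications.

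**Working it through.** The documents contain no correlation, threshold or heat-effect size, so there is no figure of theirs to reproduce. The check asks how well a prediction with no heat effect (H = 1) correlates with a truly heated profile.

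**Inputs from the documents.** Wear 19 h; heat for 1 h from 11 h (early) or 18 h (late) (Protocol Summary, section 4). The 23 post-application sampling times (section 7.2). Half-life about 24 h (section 4).

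**Assumptions.** One compartment, constant input without lag; half-lives of 4 and 8 h as alternatives; heat multiplies flux by H = 1.5, 2 or 3 during the heat hour only.

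**Formulas.** With k = 0.693/half-life, A = input rate/clearance and heat starting at s:
- Unheated: C(t) = A(1 − e^(−kt)) up to 19 h, then exponential decline.
- Added by heat: (H − 1)A(1 − e^(−k(t−s))) during the heat hour, then (H − 1)A(1 − e^(−k))e^(−k(t−s−1)).
- Heated/unheated serum ratio at the end of heat: 1 + (H − 1)(1 − e^(−k))/(1 − e^(−k(s+1))).

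A cancels from ratios and from r. At 24 h half-life, k = 0.0289, and doubled flux gives:
- early heat: 1 + 0.02847/0.2929 = 1.097
- late heat: 1 + 0.02847/0.4223 = 1.067

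A doubled flux thus moves serum by only 7% to 10%.

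**Pearson r between the H = 1 prediction and the heated profile**

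| Half-life | H | Early heat | Late heat |
|---|---|---|---|
| 24 h | 1.5 | 0.9994 | 0.9988 |
| 24 h | 2 | 0.9977 | 0.9955 |
| 24 h | 3 | 0.9919 | 0.9844 |
| 8 h | 1.5 | 0.9981 | 0.9958 |
| 8 h | 2 | 0.9929 | 0.9847 |
| 4 h | 1.5 | 0.9945 | 0.9886 |
| 4 h | 2 | 0.9803 | 0.9572 |
| 4 h | 3 | 0.9376 | 0.8582 |

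At 24 h and H = 2, the H = 1 prediction is off by −5% (early) and −6% (late) in Cmax over 0–22 h, and by −5% and −2% in AUC over 0–22 h. Error in the level is therefore also a soft test. Error in the heat-induced change is not: the predicted change is 0, so the error is (0 − Δ)/Δ = −100% in every row.

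**Sensitivity to the assumptions.**
- *Effect outlasting heat.* Early heat, H = 2, flux effect then decaying with a 3 h half-life: r = 0.98, 0.95 and 0.89 at half-lives of 24, 8 and 4 h. Counting the pre-application zero as a data point raises the last to 0.93.
- *Wider flux set.* 288 scenarios at H = 1.5 or 2, adding input lag, a skin depot and post-heat decay, with the pre-application sample included: r from 0.933 to 0.9999, median 0.9986, with 285 of 288 at 0.96 or above. The missed peak serum ratio reached 1.45.
- *Effect on serum concentration.* 288 scenarios with the same multipliers applied to concentration: r from 0.81 to 0.996 at 1.5-fold and 0.56 to 0.99 at 2-fold. Only 22% reach 0.96. Without the pre-application sample the lowest value is 0.34.

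**Is the other procedure day a clean control?** For early heat, yes over 11–18 h: the late-heat day is unheated until 18 h. For late heat, no: at 18–19 h the early-heat day is still raised by about 5% to 6% with H = 2 confined to the heat hour, and by about 26% to 38% if the effect decays with a 3 h half-life. The late-heat effect itself is only 7% at 24 h half-life.

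**The case against.** The strongest reply is that the SAP never says success will be judged by correlating heated profiles. The Level A wording is a definition in a list, and the planned plot relates fraction permeated to fraction absorbed at baseline. This stands: the defect is an absent criterion, not a wrong one that was adopted.

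A reader might infer that the planned approaches ignore heat. They do not: all three carry a heat coefficient, and H = 1 is only a benchmark. The formulas for Approach I cannot be read in the available text, so nothing is claimed about how it would perform.

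A reader might also infer that every approach would look successful, or that correlation cannot see heat at all. Neither is supported. Step 6 can be read as multiplying concentrations. With a 24 h half-life and a true 2-fold flux effect, multiplying predicted concentrations by 2 in the heat hour gives r of 0.36 (early) and 0.77 (late) against the true profile; multiplying during and after heat gives 0.96 and 0.86. Correlation can expose a badly applied coefficient. In these cases, however, the H = 1 curve scores higher still (0.998 and 0.996), which is a reason to require the benchmark.

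Finally, IVIVC is absent from the objectives, outcome measures, hypotheses and final analysis plan (sections 3.1, 3.2, 7.1, 7.3), and section 2.2 is conditional. That limits the consequence but does not remove it, because section 2.2 is where the regulatory use is stated.

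**Conclusion.** The concern holds in this form: no criterion for an established IVIVC is stated beyond Level A correlation, the Approach II and III model rests on 32°C data, and no step tests the coefficient applied at step 6. Whole-profile correlation would be a weak substitute.

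The range of about 0.96 to 0.999 for a prediction ignoring heat is conditional on one compartment, constant input and a 1.5- to 2-fold flux effect ending with the heat hour. Flux is the scale on which the SAP defines H_i, but the SAP also allows for an effect after heating, and the documents give no effect size. Under other assumptions r can be much lower, so the range should not be quoted without them.

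The patch-by-heat comparison in sections 7.1 and 7.3 does not depend on this. It should be corrected before any IVIVC conclusion about heat is drawn.

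**What to change.** In the SAP:

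1. Judge the heat part of the IVIVC by percent prediction error, per product, for the heat-induced change in Cmax and AUC over the windows already planned in section 7.2 (11–12, 12–18, 18–19 and 19–22 h). State the acceptable error in advance. Give the absolute error beside it, since a percentage is unstable when the observed change is small.
2. Require each approach to beat its own prediction with H = 1.
3. Early heat: compare 11–18 h with the same clock times on the late-heat day for the same product.
4. Late heat: compare with the model-predicted unheated curve or the pre-heat level, not with the early-heat day at 18–22 h.
5. Approach III: take the in vivo heat coefficient from products or subjects other than those used to test it, or report the result as descriptive. Testing it on the data that supplied it would be circular.
6. Report whole-profile correlation as descriptive only.

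Cost: SAP wording, an H = 1 run per approach and some held-out fitting. No new samples or procedures are needed. The IVIVC claim becomes harder to meet.

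### In Approaches II and III the baseline IVIVC model predicts the same profiles it was built on, with no product held out, so baseline agreement is optimistic as evidence about a new generic

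*SAP*

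**What the plan says.** The SAP (IVIVC) states that "Level A was selected to use for analysis of the data" and that "Three different (I, II & III) approaches were examined for Level A".

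- **Approach I.** "IVPT data, PK-based mathematical equations and in vitro heat effect coefficient (H_i) were used to predict in vivo concentrations". The clearance input reads "CL: Total body clearance obtained from literature/product package information", and the elimination rate constant has the same kind of source. No fit to this trial's concentrations is described.
- **Approaches II and III, step 1.** "Reconstruct baseline (32°C) profile by combining the non-heat (32°C) portion of each profile from the early and late heat study designs".
- **Step 2.** That baseline is deconvoluted.
- **Step 3.** "Construct an IVIVC model by plotting the fraction permeated in vitro vs the fraction absorbed in vivo".
- **Step 4.** "Predict the in vivo fraction absorbed using the IVIVC model and IVPT data".
- **Step 5.** The prediction is convoluted back to a concentration profile.
- **Step 6.** A heat coefficient is applied: the in vitro one (H_i) in Approach II, the in vivo one (H_ii) in Approach III.

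The SAP does not say whether the step 3 model is fitted per product or pooled over the three products, what functional form it takes, how predicted and observed profiles are compared, or what error would be acceptable. It names no held-out product, subject or profile. Protocol Section 2.2 gives the intended use: if an IVIVC can be established, "in vitro studies can be used for generic applications in the future", sparing volunteers further exposure.

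**The concern.** The intended use concerns a product for which there are in vitro data and no human data. Steps 1 to 5 never create that situation. The in vivo baseline goes into the model at step 3 and is what the model predicts at steps 4 and 5. Agreement between the two shows how well the model describes the products it was built on. It does not show whether in vitro differences between products carry over to in vivo differences.

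An acceptance limit alone would not cure this, because it would be applied to in-sample predictions. At stake is the inference in Section 2.2: a good baseline fit could be read as support for replacing human studies of later generics when that has not been tested.

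**Working it through.** **Where in vivo data enter each prediction**

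| Part | In vivo profile data from this trial used to build it? |
|---|---|
| Approach I | No, as described: IVPT flux, H_i, and clearance and rate constants from outside sources |
| Approaches II and III, baseline (steps 1-5) | Yes: the same non-heat data that are then predicted |
| Approach II, heated segment (step 6) | Heat effect is in vitro (H_i), applied to the baseline above |
| Approach III, heated segment (step 6) | Heat effect is in vivo (H_ii), source not stated |

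The circularity therefore lies in the baseline part of Approaches II and III. Approach III's heated segment is circular as well if H_ii comes from these subjects.

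**How much it could matter**

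The documents give no IVIVC error figure to reproduce, so the size was examined by simulation, with 600 runs per scenario. From the documents: three products, 19 h application, and fifteen sampling times from 1 to 18 h close to those in protocol Section 7.2. Everything else is assumed:

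- in vitro and in vivo flux rising as 1 - exp(-t/τ), with median τ of 6 h;
- between-product CV of 20%, 30% or 40% in both τ and steady-state flux;
- a linear Level A model on cumulative amounts (the SAP plots fractions);
- one-compartment convolution with an 8 h half-life, and noise-free profiles;
- correlation ρ between in vitro and in vivo product differences of 0 (no relation) or 0.95 (strong relation).

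Prediction error is 100 × |predicted/observed - 1|, averaged over the three products. A pass means that both the Cmax and the AUC(0-19) averages are within the limit.

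With ρ = 0, for CV 20% / 30% / 40%:

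| Check | Cmax error, % | AUC error, % | Pass at 10%, % of runs | Pass at 20%, % of runs |
|---|---|---|---|---|
| Per-product, own profile | 1.4 / 2.1 / 2.8 | 0.4 / 0.5 / 0.7 | 100 / 100 / 100 | 100 / 100 / 100 |
| Pooled, same three products | 19.1 / 25.6 / 30.8 | 17.8 / 24.9 / 31.9 | 16 / 8 / 3 | 53 / 27 / 16 |
| Leave one product out | 30.8 / 44.3 / 59.6 | 30.4 / 46.8 / 66.1 | 6 / 3 / 1 | 26 / 13 / 6 |

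The ratio of pooled in-sample error to held-out error shows the optimism of the pooled fit. For Cmax it is 19.057/30.752 = 0.62 at CV 20% and 30.782/59.577 = 0.52 at CV 40%. For AUC it is 17.819/30.448 = 0.59 and 31.933/66.054 = 0.48. In-sample error is thus roughly half to just over 60% of the held-out error.

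With ρ = 0.95, leave-one-product-out passes in 73 / 47 / 26% of runs at 10% and in 99 / 90 / 71% at 20%. It therefore separates a strong relation from none. The per-product check passes in 100% of runs under both values of ρ and separates nothing.

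**The case against.** The strongest reply is that the plan contains predictions that can fail. Approach I takes nothing from these profiles as described, so each product is a genuine prediction. Step 1 uses only non-heat data, and Approach II adds heat through H_i. Heat is the trial's question, and comparing Approach II with the observed heated data would be a real, if limited, test. This stands. A reader might infer that the whole IVIVC is circular, or that its evidence cannot fail; the documents do not support that.

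Three other inferences also go too far.

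- **That the best-looking approach will be chosen in-sample.** The SAP says the three approaches were examined. It states no rule for choosing among them, and no metric.
- **That two cumulative curves always correlate highly.** Take 1 - exp(-k(t - lag)) at the protocol's sampling times to 19 h. A curve with k = 0.1/h and lag 4 h against one with k = 0.3/h and lag 0 gives R² = 0.69. The SAP does not name R² as a criterion either.
- **That the trial is set to declare human studies unnecessary.** Section 2.2 is conditional on an IVIVC being established, and IVIVC does not appear in the objectives (3.1), outcome measures (3.2), hypotheses (7.1) or final analysis plan (7.3).

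None of this supplies a held-out product for the Approach II and III baseline, which is where the concern remains.

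**Conclusion.** The concern holds for the baseline model in Approaches II and III. Agreement there is optimistic and may make an IVIVC look established even if in vitro data cannot predict a new generic. If the model is fitted per product, this is near certain: under the simulation's assumptions, every run passed with no true relation present. If it is pooled, the effect is partial: errors are understated by roughly 40-50%, but most runs with no relation still fail a 10% limit. The SAP does not say which applies, so a reader should not infer that the IVIVC will look established whatever the truth.

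The percentages depend on assumed curve shapes, between-product variation, kinetics and error limits, and on amounts where the SAP uses fractions. They show direction and rough size; they do not forecast this trial. The reuse of the baseline and the absence of a held-out product rest on the SAP text alone.

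Approach III's heated segment, which relies on an in vivo coefficient, is not evidence that in vitro data predict the heat effect, whatever the baseline result.

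**What to change.** Amend the IVIVC section of the SAP as follows.

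1. For Approach II, fit one pooled model on two products. Predict the third product's profile from its IVPT data and H_i, and repeat so that each product is held out once (three fits).
2. Report percent prediction error for Cmax and AUC, separately for the baseline and heated segments, beside Approach I's direct prediction errors, which need no refitting.
3. Fix the error limit before the comparison is made.
4. Label in-sample fit as internal only. Base any claim that in vitro data can stand in for human studies on the held-out errors, and not on in-sample fit or on Approach III.
5. State the source of H_ii.

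The cost is SAP wording and three model fits, with no new data. Two limits should be stated with the results. Three products give only three held-out errors. The Apotex bioavailability is borrowed from the other two products, (0.36 + 0.42)/2 = 0.39, so a held-out Apotex prediction that uses it carries an assumed value. This is a cheap improvement worth making.

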	• Procedure Day 1: The heating pad will be set to induce a skin temperature of 42.0 \pm 2°C and applied for 1 hour, 11 hours after application of the Apotex (fentanyl) transdermal patch (25 µg/h).	
	• Procedure Day 2: The heating pad will be set to induce a	

skin temperature of 42.0 \pm 2°C and applied for 1 hour, 18 hours after application of the Apotex (fentanyl) transdermal patch (25 µg/h).

- Procedure Day 3: The heating pad will be set to induce a skin temperature of 42.0 ± 2°C and applied for 1 hour, 11 hours after application of the Duragesic[®] transdermal patch (25 µg/h).
- Procedure Day 4: The heating pad will be set to induce a skin temperature of 42.0 ± 2°C and applied for 1 hour, 18 hours after application of the Duragesic[®] transdermal patch (25 µg/h).
- Procedure Day 5: The heating pad will be set to induce a skin temperature of 42.0 ± 2°C and applied for 1 hour, 11 hours after application of the Mylan (fentanyl) transdermal patch (25 μg/h).
- Procedure Day 6: The heating pad will be set to induce a skin temperature of 42.0 ± 2°C and applied for 1 hour, 18 hours after application of the Mylan (fentanyl) transdermal patch (25 μg/h).

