4 STUDY DESIGN

This is an open-label, non-placebo controlled pharmacokinetic (PK) assessment study. The study will consist of six-procedure days (10 subjects) with at least two weeks between procedure days. The half-life of fentanyl is approximately 24 hours. Hence, 7 days (i.e. 5 half-lives) will be sufficient for >95% of fentanyl to be eliminated from the body. Each of the 10 subjects will be enrolled to complete all six procedure days (Procedure Days 1 to 6). The study is open label and not blinded, because PK assessment is not subject to participant and/or observer bias. After each procedure session (procedure day) is completed, the available safety data will be reviewed by an Independent Safety Monitor (ISM) to determine whether or not to proceed to the next procedure day.

The six procedures days are as follows:

Procedure Day 1: An **Apotex** (fentanyl) patch will be applied without heat for 11 hours, then a theratherm® heating pad will be applied over it (see details in Manual of Procedures) and set to induce a skin temperature of $42.0 \pm 2^{\circ}$ C for 1 hour then removed, and the patch will be kept on for another 7 hours (patch will be applied for a total of 19 hours), then it will be removed. Each subject will receive a naltrexone hydrochloride 50 mg oral tablet 12 ± 1 hour and shortly prior to patch application and then every 12 ± 1 hour for 8 additional doses, then one dose every 24 ± 2 hours for two more doses. A total of twelve 50 mg oral doses of naltrexone will be administered.

Procedure Day 2: An **Apotex** (fentanyl) patch will be applied without heat for 18 hours, then a theratherm® heating pad will be applied over it and set to induce a skin temperature of $42.0 \pm 2^{\circ}$ C for 1 hour, then the patch and the heating pad will both be removed (patch will be applied for a total of 19 hours). Each subject will receive a naltrexone hydrochloride 50 mg oral tablet 12 \pm 1 hour and shortly prior to patch application and then every 12 ± 1 hour for 8 additional doses, then one dose every 24 ± 2 hours for two more doses. A total of twelve 50 mg oral doses of naltrexone will be administered.

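### SAP, IVIVC, Approach II: H_i is a ratio of in vitro fluxes, but in the numbered order it is applied after convolution to concentration; with 1 h of heat this is not in general equivalent to heating the input

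*SAP*

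**What the plan says.** The SAP selects Level A, "Level A: a point-to point correlation between in vitro and in vivo profiles", and examines three approaches to it. H_i is the "In vitro heat effect coefficient (composite heat effect during and after heat exposure); ratio of flux values with heat and without heat".

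Approaches II and III share six numbered steps. Steps 1 to 3 rebuild the 32°C baseline, deconvolute it and relate the fraction permeated in vitro to the fraction absorbed in vivo. Step 4 is "Predict the in vivo fraction absorbed using the IVIVC model and IVPT data". Step 5 is "Convolute the predicted in vivo fraction absorbed data using Phoenix® to obtain concentration vs time profile". Step 6 applies the "in vitro heat effect coefficient H_i (Approach II) or the in vivo heat effect coefficient H_{ii} (Approach III) to the predicted in vivo profile". Heat is mentioned for the first time in step 6.

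In the Protocol Summary, the early-heat pad is "applied for 1 hour, 11 hours after application of the Apotex (fentanyl) transdermal patch", and the other two products follow the same timing. On late-heat days the pad goes on at 18 h; section 4 adds: "then the patch and the heating pad will both be removed (patch will be applied for a total of 19 hours". The only half-life given is in section 4, in the washout argument: "The half-life of fentanyl is approximately 24 hours".

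**The concern.** A flux ratio is a property of the input rate. The concentration at any moment also contains drug absorbed before heat began, which heat has not changed. If the input rate doubles for one hour at 11 h, the concentration at 12 h does not double unless nothing absorbed earlier is still present. When heat stops, concentration stays raised after the flux ratio has fallen. A multiplier on the input scale, applied to concentration, can therefore be too high during heat and too high or too low afterwards.

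This matters because Level A is judged point by point, and section 7.2 samples every 10 minutes through most of each heat hour. Section 2.2 hopes that an established IVIVC would let in vitro studies serve future generic applications. If the steps are followed in order, Approach II may misfit, or fit by chance, because of where H_i enters. The comparison would then say less than it should about the in vitro data.

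**Working it through.** The plan gives no H_i value, no predicted heated concentration and no disposition values for the convolution, so there is no figure of its own to reproduce. The check compares the two orders of operation.

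**The two orders.** Let R(s) be the unheated input rate, U the unit impulse response and H(s) the heat ratio.

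- Heat on input, then convolution: C_A(t) = ∫ R(s) H(s) U(t−s) ds.
- Convolution, then heat (the numbered order): C_B(t) = H(t) ∫ R(s) U(t−s) ds.

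They agree if H is constant over the whole wear period. They nearly agree at the end of heat if disposition is very fast relative to 1 h. Otherwise they generally differ.

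**Inputs from the documents.** Heat lasts 1 h, starting at 11 h or 18 h; wear is 19 h; half-life is about 24 h (section 4, given for washout).

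**Assumptions.** One compartment; constant baseline input; in vivo input ratio equal to the in vitro ratio; half-lives 24, 7, 3 and 1 h; all values of H.

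**Share of concentration that comes from the heat hour.** With k = ln 2 / half-life and T the end of heat (12 or 19 h):

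f = (1 − e^(−k)) / (1 − e^(−kT)).

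For 24 h, k = 0.02888. At 12:00, f = 0.02847 / 0.29289 = 0.0972. At 19:00, f = 0.02847 / 0.42232 = 0.0674.

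**Case 1: input ratio 2 for exactly 1 h, no residual effect.** The true concentration ratio at the end of heat is 1 + (H − 1)f, and the error from multiplying by H is H / [1 + (H − 1)f] − 1. For 24 h at 12:00 this is 2 / 1.0972 − 1 = 82%.

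| Half-life (h) | f at 12:00 | True ratio, 12:00 | Error, 12:00 | f at 19:00 | Error, 19:00 |
|---|---|---|---|---|---|
| 24 | 0.097 | 1.10 | +82% | 0.067 | +87% |
| 7 | 0.136 | 1.14 | +76% | 0.111 | +80% |
| 3 | 0.220 | 1.22 | +64% | 0.209 | +65% |
| 1 | 0.500 | 1.50 | +33% | 0.500 | +33% |

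**Case 2: gradual onset and decay, early heat.** The flux ratio is g(t) = 2 − e^(−(t−11)) from 11 to 12 h, then 1 + 0.632 e^(−(t−12)) up to 19 h. The true concentration ratio is 1 + k ∫ (g(s) − 1) e^(−k(t−s)) ds / (1 − e^(−kt)), integrating from 11 h to t. At 12:00, g = 1.632 while the true ratio is 1.036, 1.051, 1.084 and 1.202 (half-lives 24, 7, 3, 1 h). Multiplying concentration by g overstates by 58, 55, 51 and 36%. At 13:00, g = 1.2325 and the error is +15.3, +12.5, +7.1 and −4.4%, so the sign can change.

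**A composite H_i.** The SAP calls H_i a composite over the periods during and after heat but does not say how it is formed. If it were the average flux ratio over 11–19 h, case 1 gives (1×2 + 7×1)/8 = 1.125; the mean of g in case 2 is also 1.125. The error is 1.125 / (true concentration ratio) − 1:

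| Half-life (h) | Case 1, 11:05 | Case 1, 12:00 | Case 2, 11:05 | Case 2, 12:00 |
|---|---|---|---|---|
| 24 | +12% | +3% | +12% | +9% |
| 7 | +11% | −1% | +12% | +7% |
| 3 | +10% | −8% | +12% | +4% |
| 1 | +7% | −25% | +12% | −6% |

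At 11:05 concentration has barely moved (true ratio 1.009 in case 1 at 24 h), so a multiplier applied from the start of heat is too high there.

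**The case against.** Four points on the other side carry weight.

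1. *The operation is not spelled out.* Step 6 says only that the coefficient is applied, and its profile could loosely mean the fraction absorbed of step 4. That reading is possible but runs against the numbering, since a concentration profile already exists by step 6. If it was meant, the step order needs correcting.

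2. *The large figures use a ratio that the SAP does not define.* This stands. A reader might infer that Approach II overstates heated concentrations by 82%. The documents do not support that: the figure takes a during-heat ratio of 2, whereas the SAP's H_i is a composite. Under the assumed composite the errors are smaller and of either sign.

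3. *One compartment with a 24 h half-life favours a large error.* This also stands. The SAP separates elimination constants after IV and transdermal dosing without giving values, so 24 h may not be the value relevant to convolution. Two illustrative biexponential responses with a during-heat ratio of 2 give true early-heat ratios of 1.37 and 1.29, an overstatement of about 46% and 55% (2/1.37 − 1 and 2/1.29 − 1). The mismatch shrinks but remains.

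4. *Heating the input is the right benchmark only if the in vitro ratio carries over to in vivo input.* Section 2.1 links heat to cutaneous blood flow and a higher absorption rate, so it may not. This limits what the fix can promise; it does not make the two orders equivalent.

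A reader might also extend the point to all three approaches, or clear the other two. Neither is supported: the Approach I equations are missing from the available text, and H_ii is not defined there.

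**Conclusion.** The point holds for Approach II as its steps are numbered. A flux ratio is applied to a concentration profile, and with 1 h of heat that does not in general give the profile obtained by heating the input. The conclusion rests on the SAP's own definition of H_i, its step order and linear disposition; it does not depend on any particular H or half-life.

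The size and sign cannot be determined from the documents. The calculated range, +82% to −25% at 12:00 for early heat, comes entirely from assumed heat ratios and disposition, and shows only that the choice can matter for a point-to-point comparison.

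The consequence is bounded. IVIVC is not among the outcome measures in section 3.2, and the patch-by-heat test in sections 7.1 and 7.3 does not use H_i. Approach II should be corrected before its fit is taken as evidence for or against predicting heat effects from in vitro data.

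**What to change.** Bring heat into Approach II before step 5, in one of two ways:

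- pass the heated IVPT profile through the step-3 IVIVC model in step 4; or
- if that model is linear without time scaling, multiply the predicted input rate (increments of the fraction absorbed) by the time-specific in vitro flux ratio during and after heat.

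Then convolute. State in step 6 which profile H_i acts on and how. If application to input was already intended, correct the step order to say so.

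This removes the ordering error. It does not guarantee agreement with observed concentrations, because the heat effect in vivo may differ from that in vitro; any remaining misfit would no longer come from the step order.

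The cost is heated IVPT profiles or time-specific flux ratios in place of the composite coefficient, and a re-run of the Approach II Phoenix steps. No new subject data are needed and the primary analysis is unchanged. The SAP should also define H_ii and the scale on which it acts, so that Approach III can be checked for the same issue.
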